fresh, frozen and canned fruits and vegetables, whole grains, dairy / dairy substitutes, proteins (e.g., frozen meat/fish, beans, eggs), and dry goods (e.g., cooking oil, spices). Foods will be priced below the cost of local supermarkets (~10% below) and purchases can be made with cash, SNAP/EBT, or credit/debit. The state funded Market Bucks program will provide a dollar-for-dollar match, up to \$10, for produce purchases made with SNAP benefits. Customers will be able to enroll in a “Market Members” loyalty card program that provides incentives for shopping more frequently (e.g. \$5 off every third trip) and all customers will be asked at the point of sale if they are a Member. Community engagement will continue during this time; market staff will check in with site partners regularly to ensure smooth service, addressing any challenges and capitalizing on opportunities (e.g., community events to promote the market) in real time. Intervention site participants will be contacted monthly (e.g., sent a newsletter on the market offerings/sales) in addition to retention contacts described above.

[figure not shown]
As a note, this the start-up and implementation of the mobile market occurs at new Mobile Market sites that are starting up or that are receiving ongoing service unrelated to the trial as well – thus, this step (aside from the randomization) is not different than would/does occur normally with mobile market start-up at a new location.

Waitlist control. Sites randomized to the waitlist will not receive market service prior to follow-up data collection. After follow-up Wave 1 data collection, Wave 1 waitlist sites will participate in community engagement and then receive the market. After follow-up Wave 2 data collection, Wave 2 waitlist sites will do the same. After follow-up Wave 3 data collection, Wave 3 waitlist sites will do the same. The use of a waitlist control was purposeful and informed by our community partners. We will be in communication with waitlist site participants during the 6-month implementation period at the intervention sites, as described above to ensure up-to-date contact information and to facilitate engagement/retention.

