For sites that may be interested, a research team member and Co-Investigator [name] will go through a formal conversation using the site screening script to guide the conversation. Please see the site screening script attached.

When sites would like to join:

If an interested site were to be interested, eligible and decide to participate, a letter of support would be written documenting this decision. This letter of support will be provided to the UMN IRB following signature.

Sites meeting site eligibility criteria will be recruited in three waves, with 4 sites in wave 1, 4 sites in wave 2, and 4 sites in wave 3. After baseline data collection for each Wave, stratified randomization of sites by type (e.g., randomization within public housing, low-income senior living sites) will be conducted to ensure balance between groups. See support letters from sites on the market waitlist meeting the aforementioned criteria.

Human subject recruitment will occur in the participating communities.

In order to be eligible to participate in this study, an individual must meet the following criteria:

- (a) being aged 18 years or older;
- (b) identifying as the primary food shopper in their household;
- (c) being able to speak English or American Sign Language (ASL);
- (d) living within a half mile of the community site location; and
- (e) reporting to be likely or somewhat likely to shop at the market in response to:
“how likely would you be to shop regularly at the Twin Cities Mobile Market if it came to your neighborhood each week (response options: likely to unlikely).
- (f) willing and able to participate in all study data collection activities
 - Please note: we may be amending these inclusion criteria and this protocol and all documents to include individuals who speak other languages once the community sites are selected and the other languages are known.

9.2 Exclusion Criteria: An individual who meets any of the following criteria will be excluded from participation in this study:

- (a) planning to move in the next 12 months
- (b) not currently shopping at the mobile market
- (c) not having a phone number or mailing address
- (d) presence of a condition or abnormality that would prohibit participation in the study or the quality of the data

9.3 Screening: Screening will occur in person or via phone using the eligibility screening script (attached). Participants will self-report answers to these questions.

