Full-Service Mobile Market Intervention Risks and Protections: The full-service mobile market intervention is a community level intervention that already exists in the Twin Cities metropolitan area (there are 24 current weekly stops). While the full-service mobile market intervention will be newly available to the community sites participating in the proposed trial, the risk of participation in the mobile grocery store is minimal and equal to participation in mobile market service not associated with the trial. For example, participants of the trial will have the same opportunity to use the mobile market as will their neighbors who may or may not be in the trial. In addition, the mobile market staff on the full-service mobile market will not know (or have access to data to know) whether customers are participants in the trial or not; thus, accidental disclosure of study participation by staff will not be possible.

14.2 Reproduction Risks: Not applicable.

14.3 Risks to Others: Not applicable.

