- As a result of participation at the level of co-investigator, [name] has completed the Human Research: Social / Behavioral or Humanist Research Investigators and Key Personnel training. She will complete the required HIPAA confidentiality training as well.
- Other mobile market staff will provide regular mobile market service at the community sites recruited for this trial. This service will be the same service they provide at their other community site locations that currently receive service (those that are active an ongoing, not part of the study) and service at the community sites of this trial will be open to the general public (not just those enrolled in the study). Because the staff's involvement is limited to providing a service that is currently being provided in the city, these mobile market staff will receive a training on research ethics and the process and protocols of the study by the researcher or designated research staff in case a participant self-identifies themselves to a staff member while on the mobile market and has a question about the research study. In this case, the mobile market staff will be trained to refer these individuals to the researcher if the question is about research.
- To align our work with community engaged research principles, we seek to make sure the research process is as smooth and friendly to potential research participants as can be. Thus, the Mobile Market in partnership with university research staff/investigator(s) will be hosting informal community meetings with ongoing customers at existing non-research sites. These individuals are NOT potential research participants to discuss what works on the mobile market, what could be improved to make mobile market service even better, and to inform the proposed research processes (e.g., review of flyers,

recruitment/retention plans, participant flow through data collection experience, data collection instruments for ease of use, etc.). Community members who take part in these meetings will receive a light meal (breakfast or lunch) and a \$20 mobile market gift card for their time in the meeting and a t-shirt (if they have not already received one).

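### Exclusion criterion 9.2(b) is inverted: as written, only people who already shop at the mobile market can enrol

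*Combined protocol and SAP*

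**What the plan says.** Section 9.2 (Exclusion Criteria) opens with the rule "An individual who meets any of the following criteria will be excluded from participation in this study". Four items follow. Item (b) is "b) not currently shopping at the mobile market". Its neighbour is "c) not having a phone number or mailing address", and the other two concern plans to move and conditions that would interfere with participation or data quality.

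Other sections describe who is meant to enter and what they are exposed to:

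- Section 9.1, inclusion criterion (e), requires a favourable answer to "how likely would you be to shop regularly at the Twin Cities Mobile Market if it came to your neighborhood each week".
- Section 14.1 states that "the full-service mobile market intervention will be newly available to the community sites participating in the proposed trial".
- Section 4.1 states that "Sites randomized to the waitlist will not receive market service prior to follow-up data collection".
- Section 23.3 describes "hosting informal community meetings with ongoing customers at existing non-research sites" and says of those attending: "These individuals are NOT potential research participants".

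No section makes current market use a condition of entry.

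**The concern.** Eligibility criteria decide who is randomized, so this is an operative rule. If it is followed literally, both arms consist of people who already use the market at some other stop. Their baseline diet recalls, food security answers and purchase records would be collected under exposure to the intervention. The primary analysis in section 17.3 compares baseline-to-follow-up change in HEI-2015 between arms. In such a sample it would measure the effect of adding a nearer stop for existing customers, not the effect of bringing the market to people who lack it.

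If screeners instead apply the opposite rule because the intent is obvious, each non-shopper they enrol meets a written exclusion and is an eligibility deviation on paper. The published criteria would also misdescribe the enrolled sample. The text fails in either case.

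**Working it through.** There is no figure to reproduce. The check is a literal reading of 9.2(b), set against the rest of the protocol.

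**Step 1: the logic of the item.** The rule is that meeting any item means exclusion. Item (b) is met by a person who does not currently shop at the market. So a non-shopper is excluded, and an eligible person must be a current shopper.

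**Step 2: could the list be read as entry conditions?** If the items were conditions a participant must satisfy, (b) would say what the design needs. The lead-in rules this out, and so does item (c), which has the same negative form and is a true exclusion: lacking a phone number or mailing address keeps a person out. Reading (b) as an entry condition would require reading (c) as one too, which is absurd.

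**Step 3: compare the literal population with the design.**

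| Section | What it implies about participants at entry | Fit with literal 9.2(b) |
|---|---|---|
| 9.1, inclusion (e) | Market service in the neighbourhood is hypothetical | Poor |
| 14.1 | The market is new to the trial sites | Poor: a current shopper must be using a stop elsewhere |
| 4.1, start-up | Residents are introduced to how the market works | Poor: customers already know |
| 4.1, waitlist control | Control sites are unserved until follow-up | Poor: controls would enter already exposed |
| 2.2, feasibility study | People recruited from market waitlist sites served as the non-customer comparison | Opposite |
| 1.1, Aim 3 | Adoption of market shopping is to be explained | Opposite: all would have adopted before entry |
| 5.2, process measures | Market trips at baseline and follow-up are recorded as contamination and dose | Poor: prior use would be universal |
| 23.3 | Ongoing customers who attend meetings at existing sites are not potential participants | Supporting only, as it concerns one group |

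**Step 4: consequence for recruitment.** Section 5.1 plans 12 sites with 22 participants each, and 12 × 22 = 264, the enrolment target in 11.1. Inclusion (d) requires residence within half a mile of the trial site. Under the literal rule, each site would have to find 22 primary household shoppers who live that close to a site the market does not yet visit and who already use another of its stops. The protocol mentions 24 existing weekly stops but does not say how many of their customers live near trial sites. The difficulty is therefore clear in direction but cannot be quantified.

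**Step 5: size.** By the wording, 100% of enrolled participants, controls included, are market users at baseline. With *not* removed, 0% are. Both follow from the rule itself.

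**The case against.** The strongest reply is that this is a drafting slip that nobody could act on. The surrounding design makes the intent plain, and a rule that would leave few eligible people at unserved sites would be noticed on the first day of screening. Section 9.3 says screening uses an attached script. That script is not in the documents reviewed and may already ask the question the right way round. On this view nothing in the trial's contrast is actually at risk.

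Parts of this stand:

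- The rule applied in the field cannot be seen, so there is no evidence that anyone was wrongly enrolled.
- The conflict with inclusion (e) is strong tension, not strict contradiction: a customer of another stop can still say how likely they would be to shop at one in their own neighbourhood.
- Controls can travel to other stops under either wording, since those stops are open to anyone. Correcting (b) keeps existing users out at entry but does not remove that access.
- The intended rule is inferred from the design, because no other section states an individual no-current-shopping criterion.
- Nothing in the power or sample-size statements of sections 11.1 and 17.2 depends on this item.

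None of this rescues the text. That a reader can guess the intent does not make an inverted criterion acceptable in the governing document. An unseen script is a reason to check it, not a reason to leave the protocol as it is.

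**Conclusion.** The concern holds. Section 9.2(b) as written admits only current market shoppers, no other section corrects it, and the rest of the protocol describes a trial in people newly offered the market. The likely cause is a stray *not*, or an inclusion condition moved into the exclusion list without being reversed.

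The error is complete in direction: all enrolled participants exposed at baseline under the wording, none under the evident intent. Harm to the treatment contrast is conditional on literal application. The mismatch between the written rule and any sensible enrolment is not conditional. The conclusion rests on the plain meaning of the lead-in and item (b), and on inferring the intended rule from the design. It must be fixed, because eligibility text is operative and an inverted rule defines the wrong population.

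**What to change.** Delete *not* from 9.2(b), so that current market shoppers are excluded. Alternatively, move the phrase as it stands to 9.1 as an inclusion criterion. Use one of these, not both.

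Then check that the eligibility screening script asks about current market use in the corrected direction. If anyone has already been screened, review those records against the corrected rule. Document any existing customers who were enrolled, and record that non-shoppers enrolled under the uncorrected wording were in line with the intended criterion.

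The cost is a one-word amendment submitted to the IRB, a check of one script and, if screening has begun, a review of the screening log. No change to the sample size or the analysis plan follows.

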10.0 Vulnerable Populations

10.1 Vulnerable Populations:

Population / Group	Identify whether any of the following populations will be targeted, included (not necessarily targeted) or excluded from participation in the study.
Children	Excluded from Participation
Pregnant women/fetuses/neonates	Included/Allowed to Participate
Prisoners	Excluded from Participation
Adults lacking capacity to consent and/or adults with diminished capacity to consent, including, but not limited to, those with acute medical conditions, psychiatric disorders, neurologic disorders, developmental disorders, and behavioral disorders	Included/Allowed to Participate
Non-English speakers	Included/Allowed to Participate
Those unable to read (illiterate)	Included/Allowed to Participate
Employees of the researcher	Included/Allowed to Participate
Students of the researcher	Included/Allowed to Participate

SOCIAL PROTOCOL (HRP-580)**PROTOCOL TITLE: Mobile Food Market Cluster Randomized Trial****VERSION DATE: 1/5/2023**

Undervalued or disenfranchised social group	Targeted Population
Active members of the military (service members), DoD personnel (including civilian employees)	Included/Allowed to Participate
Individual or group that is approached for participation in research during a stressful situation such as emergency room setting, childbirth (labor), etc.	Excluded from Participation
Individual or group that is disadvantaged in the distribution of social goods and services such as income, housing, or healthcare.	Targeted Population
Individual or group with a serious health condition for which there are no satisfactory standard treatments.	Included/Allowed to Participate
Individual or group with a fear of negative consequences for not participating in the research (e.g. institutionalization, deportation, disclosure of stigmatizing behavior).	Included/Allowed to Participate
Any other circumstance/dynamic that could increase vulnerability to coercion or exploitation that might influence consent to research or decision to continue in research.	Excluded from Participation

10.2 Additional Safeguards:

- This study is not recruiting based on pregnancy status. Rather, it is possible that a pregnant women would meet all criteria for inclusion in the study, given the nature of this research, there is no anticipated harm to pregnant women or the fetus, should she elect to enroll in the research.

SOCIAL PROTOCOL (HRP-580)

PROTOCOL TITLE: Mobile Food Market Cluster Randomized Trial

VERSION DATE: 1/5/2023

- Because the study will be recruiting in the community, no prisoners will be included.
- No individuals less than 18 years of age are included based on inclusion criteria.
- We do not anticipate enrolling individuals with impaired capacity to consent. Assessment of capacity to consent will be informally made during routine interactions with participants. No specific assessment or documentation of capacity is required under those circumstances.
- American Sign Language speakers will be allowed to participate in this study, though they will not be specifically targeted for recruitment. If an ASL speaker indicates interest in the study while we are conducting recruitment, we will contact a certified interpreter to facilitate communication. An interpreter will be used for all study visits and be available to the participant if they have questions regarding any written forms. We will have an interpreter translate our consent form into a video, a link to which will be provided on the English consent form. In addition, if preferred by the participant, we will allow ASL speakers to conduct their follow-up dietary recalls in person with an interpreter rather than requiring these to be conducted by phone and will allow the interpreter to interpret the iPad written survey questions as read by a study staff member and the participant's responses so they can be entered. Additional non-English speakers may be targeted for recruitment at a later time, but the languages are not yet known. We will amend this protocol/procedures and all related documents once the languages are solidified to add this inclusion criterion and related supporting documentation (e.g., consent form in selected languages etc) and will wait to receive IRB approval related to this modification prior to enrolling participants who do not speak English.
- This study will not be targeting recruitment of individuals who are not literate. However, if an individual who is not able to read wants to participate, study staff will assist with completion of surveys, forms, etc. to ensure that the sample is inclusive of and represents all individuals that wish to use the mobile market including any that may not be literate. Participants who are illiterate may not be known, research staff will not be asking a direct question about literacy to potential participants. However, if it is made known to us that the participant is illiterate we will take extra care to go through the consent form and read it to the potential participant. An unbiased witness (non-study team member) will be present to attest that the consent form was described accurately. He/she will also sign the consent form.
- Employees of the researcher: If an employee of the researcher presents as a potential participant eligible for this study, they will be seen for consenting and treatment by a member of the study team who is not the researcher. They will

SOCIAL PROTOCOL (HRP-580)

PROTOCOL TITLE: Mobile Food Market Cluster Randomized Trial

VERSION DATE: 1/5/2023

be told during consenting that their decision whether to participate will not affect their professional relationship with the researcher.

- Student of the researcher: If a student of the researcher presents as a potential participant eligible for this study, they will be seen for consenting by a member of the study team who is not the researcher. They will be told during consenting that their decision whether to participate will not affect their professional relationship with the researcher nor will it have an impact on their graduation status, GPA, future job or internship opportunities or any other academic or professional status.
- This study will recruit individuals who are disadvantaged in the distribution of social goods and services such as income, housing or health care and/or who may identify as an undervalued or disenfranchised social group. In particular, the mobile market aims to serve those who live in low-income, low food access communities; thus, it is critically important that the population the mobile market is trying to reach is included in the study, as it will ensure the results represent the target population. Caution was taken to provide appropriate levels of compensation for participants given their income level, so as to not be coercive while also providing appropriate compensation for the time spent in research activities. Levels were set in conjunction with community partner. When possible, diverse and multilingual research staff will be hired to reflect the individuals in the community site locations.
- Active members of the military (service members), DoD personnel (including civilian employees): Members of the military may not be known, research staff will not be asking a direct question about military status to potential participants. We do not anticipate vulnerability for this group to be increased by participating in this study.
- Individual or group with a serious health condition for which there are no satisfactory standard treatments: Participants with a serious health condition for which there is not satisfactory standard treatment will be fully informed of the potential risks and benefits of the research study. We do not anticipate vulnerability for this group to be increased by participating in this study.
- Individual or group with a fear of negative consequences for not participating in the research (e.g. institutionalization, deportation, disclosure of stigmatizing behavior): Individuals with a fear of negative consequences for not participating in the research (e.g. institutionalization, deportation, disclosure of stigmatizing behavior) are not targeted but may be enrolled. All participants will be fully informed that the study is completely voluntary and that they may withdraw participation at any time.

10.3 If research includes potential for direct benefit to participant, provide rationale for any exclusions indicated in the table above:

Prisoners are excluded as they will not have access to the mobile market while in custody. Children are excluded as they are not the primary food purchasers in this household, which is whom this intervention is targeted for – they may still benefit

SOCIAL PROTOCOL (HRP-580)

PROTOCOL TITLE: Mobile Food Market Cluster Randomized Trial

VERSION DATE: 1/5/2023

if their parent/guardian enrolls in the study. We are not including people in a stressful time sensitive situations like being in the emergency room or while in labor, as they are not the target population of the mobile market; these individuals would be eligible to participate when the stressful situation has resolved if meeting eligibility criteria.

As a reminder: Non-English speakers, with the exception of ASL speakers, will be excluded from participation at this time. However, they may be targeted for recruitment at a later time, but the languages are not yet known. We will amend this protocol and all related documents once the languages are solidified to add this inclusion criterion and related supporting documentation and will wait to receive IRB approval related to this modification prior to enrolling participants who do not speak English.

